7.9.5 Stopping Criteria

If a patient experiences an AE assessed as \geq Grade 3 (\geq Grade 2 for the system-organ class of Cardiac Disorders) according to Common Terminology Criteria for Adverse Events (CTCAE v5), then: 1) BSI-045B treatment may be continued if the AE is considered to be unrelated to BSI-045B; 2) BSI-045B treatment will be withheld if the AE is considered to be related to BSI-045B, until the toxicity returns to \leq Grade 2; 3) BSI-045B will be permanently discontinued if the AE recurs to \geq Grade 3 after BSI-045B treatment resumed and is considered to be BSI-045B related. Treatment discontinuation decisions will be made by Investigators after a discussion with Sponsor. These AEs include hepatotoxicity, injection site reactions, allergic conjunctivitis and hypersensitivity (see Table 8). Patients who experience such AEs will be followed until the adverse events resolves or stabilizes. Study drug administration will not be discontinued.

If 2/3 of patients experience any adverse event assessed as \geq Grade 3 (\geq Grade 2 for the system-organ classes of Cardiac Disorders) per Common Terminology Criteria for Adverse Events (CTCAE v5), the study should be suspended for an evaluation from SSC.

Table 8. Toxicity with the Potential to Cause Study Treatment Discontinuation

Toxicity	Criteria	
Hepatotoxicity	 AST/ALT >5×ULN and/or Bilirubin >3×ULN Hepatic failure Recurrence of a severe or life-threatening event, or any of the laboratory abnormalities listed above, that are presumed to be study treatment related. 	
Injection site reactions	 Ulceration or necrosis; severe tissue damage; operative intervention indicated Severe reactions lasting more than 24 hours 	
Conjunctivitis*	 Symptomatic with marked decrease in visual acuity (best corrected visual acuity worse than 20/40 or more than 3 lines of decreased vision from known baseline, up to 20/200); limiting self-care Activities of Daily Living (ADL); if infectious is the etiology, intravenous antibiotic, antifungal, or antiviral intervention indicated Urgent intervention indicated or life-threatening. 	
Hypersensitivity	Anaphylaxis: Symptomatic bronchospasm, with or without urticaria; parenteral intervention indicated; allergy-related edema/angioedema; hypotension	

V4.0_8 Jul 2024 Page 45 of 68

Toxicity	Criteria	
	• Serum sickness: Severe arthralgia or arthritis; extensive rash; steroids or IV fluids indicated	
	Allergic reaction: Bronchospasm; hospitalization indicated for clinical sequelae; intravenous intervention indicated	
	Urgent intervention indicated or life-threatening.	

^{*} Definition of Conjunctivitis: a disorder characterized by inflammation, swelling and redness of the conjunctiva of the eye.

For the evaluation of injection site reactions, the following scale (Table 9) which is a part of FDA toxicity grading scale will be used.

Table 9. Grading scale for injection site reactions

Local reactions	Mild (Grade 1)	Moderate (Grade 2)	Severe (Grade 3)	Potentially life threatening (Grade 4)
Pain	Dose not interfere with activity	Repeated use of non-narcotic pain reliever > 24 hours or interferes with activity	Any use of narcotic pain reliever or prevents daily activity	Emergency room (ER) visit or hospitalization
Tenderness	Mild discomfort to touch	Discomfort with movement	Significant discomfort at rest	ER visit or hospitalization
Erythema/ Redness*	2.5-5 cm	5.1-10 cm	>10 cm	Necrosis or exfoliative dermatitis
Induration/ Swelling **	2.5-5 cm and dose not interfere with activity	5.1-10 cm or interferes with activity	>10 cm or prevents daily activity	Necrosis

^{*} In addition to grading the measured local reaction at the greatest single diameter, the measurement should be recorded as a continuous variable.

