	Pharmacokinetics listings will be provided. PK parameters might be estimated through compartmental modeling. Additionally, the PK/Efficacy relationship might be explored.										
	Immunogenicity: Anti-BSI-045B ADA during and post BSI-045B treatment.										
	PD biomarkers : Serum levels of thymus and activation related chemokine/C-C chemokine ligand 17 [TARC/CCL-17], periostin, and IgE during and post BSI-045B treatment.										
	Exploratory Endpoints:										
	 Proportion of patients with EASI90 at Week 26 (2 weeks after last dose at Week 24) 										
	 Proportion of patients with EASI50 at Week 26 (2 weeks after last dose at Week 24) 										
	Percent change from baseline in EASI at each visit										
	 Proportion of patients achieving IGA 0 or 1 at Week 26 (2 weeks after last dose at Week 24) 										
	 Percent changes in PP-NRS scores at Week 26 (2 weeks after last dose at Week 24) 										
	 Proportion of patients achieving facial IGA 0/1 at Week 26 (2 weeks after last dose at Week 24) 										
	Occurrence of conjunctivitis										
Stopping Criteria	If a patient experiences an AE assessed as ≥ Grade 3 (≥ Grade 2 for the systemorgan class of Cardiac Disorders) according to Common Terminology Criteria for Adverse Events (CTCAE v5), then: 1) BSI-045B treatment may be continued if the AE is considered to be unrelated to BSI-045B; 2) BSI-045B treatment will be withheld if the AE is considered to be related to BSI-045B, until the toxicity returns to ≤ Grade 2; 3) BSI-045B will be permanently discontinued if the AE recurs to ≥ Grade 3 after BSI-045B treatment resumed and is considered to be BSI-045B related. Treatment discontinuation decisions will be made by Investigators after a discussion with Sponsor. These AEs include hepatotoxicity, injection site reactions, allergic conjunctivitis and hypersensitivity (see Table 8).										

V4.0_8 Jul 2024 Page 13 of 68

	Patients who experience such AEs will be followed until the adverse events resolves or stabilizes. Study drug administration will not be discontinued.
	If 2/3 of patients experience any adverse event assessed as ≥ Grade 3 (≥ Grade 2 for the system-organ classes of Cardiac Disorders) per CTCAE v5, the study should be suspended for an evaluation from SSC.

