7.11 Criteria for Early Discontinuation of Study Drug

A patient has the right to withdraw from treatment at any time at his/her request and this decision will not affect the treatment provided by clinicians or research institutions in the future. Moreover, the patients may be withdrawn at any time at the discretion of the Investigators for safety, behavioral, compliance, or administrative reasons. When medically feasible, the Medical Monitor should be consulted prior to study drug discontinuation. Study drug treatment will be permanently discontinued if one of the following criteria applies:

- Withdrawal of consent
- Patient or guardian requests to discontinue the study drug
- Start of new anti-AD treatment
- Lost to follow-up
- Death
- Intolerable safety issues

V4.0_8 Jul 2024 Page 47 of 68

• AE, abnormal laboratory tests, or other medical condition (including pregnancy) occurred, and the Investigator judges that the study drug should be terminated based on the best interests of the patient

- Major noncompliance with the study protocol and in the Investigator's judgment, treatment should be discontinued
- Other conditions that the Investigator considers inappropriate for continue treatment
- Study terminated by the Sponsor

If a patient withdraws from study treatment after receiving study treatment, a safety examination is required within 7 days after the patient's withdrawal. Additional follow-up assessments should be completed.

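### Protocol 7.9.5 and the Synopsis: the closing sentence contradicts the stopping rules, and the stricter cardiac threshold does nothing at Grade 2

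*Protocol*

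**What the plan says.** Section 7.9.5 has three numbered clauses for adverse events of CTCAE Grade 3 or higher. The threshold is lowered to "Grade 2 for the system-organ class of Cardiac Disorders".

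- **Clause 1:** an unrelated event allows treatment to continue.
- **Clause 2:** "2) BSI-045B treatment will be withheld if the AE is considered to be related to BSI-045B, until the toxicity returns to" Grade 2 or lower.
- **Clause 3:** "BSI-045B will be permanently discontinued if the AE recurs to" Grade 3 or higher "after BSI-045B treatment resumed and is considered to be BSI-045B related".

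The paragraph then says "Treatment discontinuation decisions will be made by Investigators after a discussion with Sponsor". It names hepatotoxicity, injection site reactions, allergic conjunctivitis and hypersensitivity, with a pointer to Table 8, and asks for follow-up until resolution or stabilisation. It ends "Study drug administration will not be discontinued". The Synopsis carries the same clauses and the same ending.

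Table 8 lists hepatic failure, anaphylaxis and life-threatening events among its entries. Its title presents them as events that may lead to discontinuation.

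Section 7.11 says "Study drug treatment will be permanently discontinued if one of the following criteria applies". Its ten bullets include "Intolerable safety issues", an adverse event for which the Investigator judges that drug should end, and a general bullet for other conditions, also at the Investigator's discretion.

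**The concern.** This is the text a site will open when a patient has a serious reaction, so it should give one answer. A site that took the last sentence literally would keep dosing in a case where clause 2 requires a hold or clause 3 requires a stop.

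The cardiac carve-out was evidently meant to be stricter than the general rule. For an individual patient with a related Grade 2 event, it requires nothing that lasts.

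Re-dosing after a first related anaphylaxis or hepatic failure is decided case by case. Maintenance doses are two weeks apart, so an acute reaction could settle to Grade 2 or lower before the next visit. The hold alone might then change nothing.

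**Working it through.** The plan states no figure on this point, so the check is mainly a comparison of texts.

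**1. The closing sentence against the rest.** Clause 2 requires withholding. Clause 3 requires permanent discontinuation. Table 8 lists grounds for discontinuation. Section 7.11 requires permanent discontinuation when a listed criterion applies. SAP 4.8.2 plans tables of events leading to withdrawal of study drug. The unqualified sentence fits none of these. It fits only clause 1, which already permits continuation after an unrelated event.

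**2. Trigger, release and recurrence grades for related events.**

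| Class | Hold starts at | Hold may end at | Recurrence forcing a stop |
|---|---|---|---|
| All other classes | 3 or higher | 2 or lower | 3 or higher |
| Cardiac Disorders | 2 or higher | 2 or lower | 3 or higher |

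For other classes, no grade both starts a hold and permits its release. For cardiac events, Grade 2 does both. A cardiac event that recurs at Grade 2 lies below the clause 3 threshold, so it never forces a stop. The lower cardiac threshold does still count in the separate study-suspension rule (two thirds of patients). The fault is in the patient-level rule.

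**3. What fixes the outcome after a first related anaphylaxis or hepatic failure.**

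- Of the three clauses, only clause 3 mandates a permanent stop, and it needs a recurrence.
- None of the four Table 8 rows is marked mandatory at first occurrence.
- None of the ten bullets in 7.11 names either event. Three can reach a first event, through an undefined term or Investigator judgement.
- Section 10.6 requires SAE reporting within 24 hours. That brings in the Sponsor but does not itself stop dosing.
- The formal Safety Steering Committee review comes when 20 patients complete Week 12 dosing.
- The study-suspension rule needs 14 of 20 patients (2/3 × 20 = 13.3, rounded up) or 16 of 24. At an assumed 30% per-patient rate of qualifying events, the binomial chance of reaching it is about 0.03% or 0.02%. It is no safeguard against a single severe event.

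By contrast, exclusion criterion 5 would refuse entry to a patient with prior anaphylaxis to a biologic.

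**4. What an earlier stop costs the primary analysis.** Doses fall at Weeks 1, 2, 3, 4 and 6 (dose 5), then every two weeks to Week 24, which makes 4 + 10 = 14 (SAP 4.8.1). A patient who has completed dose 5 is not replaced (7.3). Follow-up ends 12 weeks after the last dose:

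- last dose at Week 6, 8, 10 or 12: follow-up ends at Week 18, 20, 22 or 24, so there is no Week 26 EASI;
- last dose at Week 14 or later: follow-up reaches Week 26, as in the SAP 4.1.4 example.

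So 4 of the 9 possible early last-dose visits from dose 5 to dose 13 lose the Week 26 value, assuming no missed dose and completed follow-up. The observed-case analysis in SAP 4.7.1 then drops that patient from the proportion. The documents give no expected EASI75 rate, so I assume 25% to 75%:

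- n = 20: 5/20 = 25.0% becomes 5/19 = 26.3% or 4/19 = 21.1%; 15/20 = 75.0% becomes 15/19 = 78.9% or 14/19 = 73.7%. The shift is 1.3 to 3.9 points.
- n = 24: 6/24 = 25.0% becomes 6/23 = 26.1% or 5/23 = 21.7%; 18/24 = 75.0% becomes 18/23 = 78.3% or 17/23 = 73.9%. The shift is 1.1 to 3.3 points.

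**The case against.** The strongest reply is that the protocol does provide for stopping at a first event. Clause 2 does not say treatment must resume. The sentence giving the decision to the Investigator comes directly before the pointer to Table 8. Table 8 lists hepatic failure, anaphylaxis and life-threatening events with no recurrence condition, and 7.11 makes the stop permanent once the Investigator so judges. Section 12.5 tells the Investigator to remove a patient from immediate hazard in an emergency. Exclusion criterion 5 makes routine re-dosing after anaphylaxis hard to attribute to the plan's intent.

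All of that stands. A reader might infer that the drug cannot be stopped after a first life-threatening reaction, or that re-dosing is required once it settles. The documents do not support either reading. Nor do they show that every first related Grade 4 event must be an automatic stop. Judgement-based stopping is a defensible choice in an open-label study of 20 to 24 patients, and some such events may be transient or laboratory-only.

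The safety record is also fair context. Phase 1 had no serious treatment-emergent events, and Section 5.6 reports no specific signal so far in this study. The numbers are small, and Phase 1 did include one severe transaminase increase and one withdrawal with raised AST and ALT.

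The closing sentence is probably an editing remnant, and a careful site would follow the clauses. That lowers the likely harm but does not remove the contradiction. Nothing in the reply repairs the cardiac grades: judgement could still extend a hold or stop the drug, but the written rule adds nothing lasting at Grade 2.

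**Conclusion.** Two faults are established from the text alone and appear in both 7.9.5 and the Synopsis: the closing sentence contradicts the rules around it, and the patient-level cardiac rule has no effect at Grade 2. Both should be fixed.

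The third element is narrower. A permanent stop after a first related anaphylaxis or hepatic failure is available but not fixed in advance. Making it mandatory is a cheap safety gain, and for anaphylaxis it agrees with the plan's own entry criterion. Extending it to all first related Grade 4 events is optional.

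The size of the problem is which action a site must take, not a rate, because the documents give no frequency for these events in patients. The 30% rate used for the suspension rule and the 25% to 75% EASI75 range are my assumptions. Neither affects the two main faults.

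**What to change.** In 7.9.5 and the Synopsis:

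- **(a)** Delete the closing sentence about not discontinuing study drug.
- **(b)** Keep clause 2 for all related events of Grade 3 or higher, on CTCAE or on the Table 9 injection-site scale, and for related cardiac events of Grade 2 or higher, unless (d) applies. Allow resumption at Grade 2 or lower, or at Grade 1 or lower for cardiac events. Leave clause 2 without an upper grade limit. Otherwise a Table 9 Grade 4 reaction, such as an emergency visit for pain, could fall under no rule.
- **(c)** In clause 3, set the recurrence threshold for cardiac events at Grade 2 or higher.
- **(d)** Add a rule that BSI-045B stops permanently at the first related anaphylaxis or hepatic failure. Mark those two Table 8 entries as mandatory and cross-refer in 7.11. Other first related Grade 4 events stay on hold until the Investigator has decided, after discussion with the Sponsor.

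With (b) and (c), a cardiac hold starts at Grade 2, ends at Grade 1 or lower, and a related recurrence at Grade 2 is a stop. The overlap is gone.

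The cost is text edits and an occasional earlier stop. If that patient's last dose is at Week 6 to 12, the Week 26 EASI may be missing. The patient stays in the Efficacy Analysis Set, and the early-withdrawal EASI and the last-observation-carried-forward sensitivity analysis in SAP 4.7.1 limit the effect. A stop made by judgement under the present text carries the same loss.

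### The stopping criteria order permanent discontinuation and then say study drug will not be discontinued; the release grade for a cardiac hold is also unclear

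*Protocol*

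**What the plan says.** Protocol 7.9.5 and the Stopping Criteria entry in the Synopsis carry the same paragraph. It applies to an adverse event of CTCAE Grade 3 or higher, or Grade 2 or higher in the Cardiac Disorders class, and gives three rules.

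- Rule 1, unrelated event: "BSI-045B treatment may be continued if the AE is considered to be unrelated to BSI-045B".
- Rule 2, related event: treatment is withheld "until the toxicity returns to ≤ Grade 2".
- Rule 3, recurrence: "BSI-045B will be permanently discontinued if the AE recurs to" Grade 3 or higher after dosing has resumed and the event is considered related.

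The paragraph goes on: "Treatment discontinuation decisions will be made by Investigators after a discussion with Sponsor". It names hepatotoxicity, injection site reactions, allergic conjunctivitis and hypersensitivity as examples, refers to Table 8 ("Toxicity with the Potential to Cause Study Treatment Discontinuation"), and says that patients with these events are followed to resolution or stabilisation. Its last sentence is "Study drug administration will not be discontinued".

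A separate study-level rule follows. If two-thirds of patients have an event at the same thresholds, "the study should be suspended for an evaluation from SSC".

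Section 7.11 states: "Study drug treatment will be permanently discontinued if one of the following criteria applies". Its list includes intolerable safety issues, and an adverse event for which the Investigator judges that stopping is in the patient's best interests. Neither ground requires the event to be related to study drug.

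**The concern.** This paragraph tells sites whether to dose a patient after a serious toxicity. For a related event that recurs at Grade 3 or higher, it first requires a permanent stop and then denies that drug is stopped. A site that looks to the Synopsis for clarification finds the same sentence there.

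The cardiac threshold raises a second, smaller question. Lowering the trigger to Grade 2 signals extra caution for cardiac events, but the release level in rule 2 was not lowered with it. An Investigator who holds drug for a related Grade 2 cardiac event is not told what improvement ends the hold.

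**Working it through.** The plan states no figure on this point, so the check is a literal reading of the text, followed by a dose count to price the fix.

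**Step 1. Which events does the closing sentence cover?** The sentence just before it speaks of patients who experience such events, meaning those the paragraph has been describing. These include the Table 8 toxicities, and the hepatotoxicity row of Table 8 itself lists recurrence presumed related to treatment. The closing sentence has no qualifier limiting it to first events, unrelated events or the follow-up interval. It therefore covers the events that rule 3 governs.

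**Step 2. What does it conflict with?**

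| Provision | Effect | Relation to the closing sentence |
|---|---|---|
| Rule 3 (7.9.5, Synopsis) | Orders a permanent stop | Direct contradiction |
| Section 7.11 | Orders a permanent stop on listed grounds, including an adverse event on Investigator judgement | Direct contradiction |
| Decision sentence (7.9.5) | Says who decides on discontinuation | Presupposes that discontinuation is possible |
| Table 8 title | Names toxicities that may cause discontinuation | Presupposes that discontinuation is possible |

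**Step 3. Apply the rules by grade to a related event.**

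| Event | Grade | Trigger met? | Release level (Grade 2 or lower) already met at onset? | Recurrence at this grade forces a permanent stop? |
|---|---|---|---|---|
| Non-cardiac | 1 or 2 | No | n/a | No |
| Non-cardiac | 3 or higher | Yes | No | Yes |
| Cardiac | 1 | No | n/a | No |
| Cardiac | 2 | Yes | Yes | No |
| Cardiac | 3 or higher | Yes | No | Yes |

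Only the cardiac Grade 2 row is inconsistent: the event triggers a hold and meets the condition for ending it at the same moment. The study-level rule has its own cardiac Grade 2 threshold and is unaffected.

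**Step 4. Doses at stake if a cardiac hold is given a lower release grade.** Protocol Table 1 and SAP 4.8.1 give dosing at Weeks 1, 2, 3, 4 and then every two weeks from Week 6 to Week 24. That is 4 + 10 = 14 doses, and 14 × 300 mg = 4200 mg, which matches the SAP total. Assume that doses falling within a hold are skipped; the protocol does not say. The worst case starts in the weekly loading phase.

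- 4-week hold after dose 1: Weeks 2, 3 and 4 are missed, 3/14 = 21%.
- 8-week hold after dose 1: Weeks 2, 3, 4, 6 and 8 are missed, 5/14 = 36%.
- 4-week hold after dose 13: only Week 24 is missed, 1/14 = 7%.

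Neither figure is an upper bound, since hold length is not capped and a hold could be repeated.

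**The case against.** The best defence is that the closing sentence was meant narrowly. The paragraph distinguishes withholding from permanent discontinuation, and the sentence follows the instruction to follow patients until the event resolves. It could mean that during follow-up of a first event drug is held but not discontinued, with rule 3 and Section 7.11 as exceptions. That may well be what was intended, but the text does not say so, and a safety instruction should not depend on the reader supplying the limit. Confining it to unrelated events would not work either: it would turn the permission in rule 1 into an order and would still conflict with Section 7.11.

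It is also fair to say that the practical risk is small. Rule 3 is specific, Section 7.11 secures stopping independently, and Investigators decide with the Sponsor. Section 5.6 reports no specific safety signals in this study up to the amendment. This stands, and it limits the weight of the point.

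On the cardiac rule, a reader might infer that a related Grade 2 cardiac event requires no dose to be withheld. That is one literal reading, but the documents do not establish it. Rule 2 says that treatment will be withheld for a related event, and its reference to toxicity returning to a level implies that some hold was intended. What the text supports is that the release grade is unclear.

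**Conclusion.** The closing sentence is wrong as written, in both places. It contradicts rule 3 and Section 7.11, and it does not fit the decision sentence or the Table 8 title. It should be corrected because it is a dosing instruction after severe related toxicity, although mistaken re-dosing is unlikely.

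The number of patients affected cannot be estimated from the documents. Phase 1 reported one severe treatment-emergent event among 54 assessed participants (Section 5.6). That counts a first event, mostly in healthy volunteers given one to five doses, and says little about related recurrence under 14 doses.

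The cardiac point is secondary and confined to the individual-level rule: trigger and release meet at Grade 2, so the end of a hold is undefined. No cardiac event rate is given.

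Two stronger conclusions might be inferred and are not supported. One is that many separate provisions order drug to be stopped: only rule 3 and the Section 7.11 grounds do. The decision sentence and the Table 8 title merely presuppose discontinuation, and the SAP 4.8.2 table of events leading to withdrawal is a reporting table. The other is that any analysis is compromised: no endpoint, analysis set or estimate depends on this sentence.

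**What to change.** Make the same two edits in Section 7.9.5 and in the Synopsis.

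1. Delete the closing sentence. Do not re-scope it to unrelated events. This changes no doses, assessments or analyses.
2. In rule 2, add a release level for Cardiac Disorders: withhold until Grade 1 or lower, or baseline. Other events keep release at Grade 2 or lower.

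Whether a related cardiac event recurring at Grade 2 should lead to permanent discontinuation is a clinical decision. Until it is settled, such an event could be held, resumed and recur with no rule-based stop, so the clinical team should address it at the same time. Rule 3, the study-level suspension rule, Section 7.11, Table 8 and the SAP tables can stay as they are.

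The cost is one amendment, which under Section 12.1 needs the same review as the original protocol, or a clarification letter of the kind mentioned in Section 12.5 if that route is acceptable. The second edit also costs whatever doses fall within a cardiac hold, if they are skipped; the amendment should state whether they are.
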